COVER PAGE

Title: A trauma-Informed Adaptation of Mindfulness-Based Relapse Prevention for Women in
Substance Use Treatment

NCT03505749

Document Date: 02/29/2020

PROCEDURES AND STATISTICAL ANALYTIC PLAN

This goal of this study was to develop and implement an integrated intervention protocol for a feasibility and initial efficacy trial of TI-MBRP. During the treatment development phase, information was gathered from focus groups with counselors and patients. The trial determined feasibility, acceptability and initial efficacy, explored mediators and moderators of change, and informed the design for a larger randomized-control trial.

The study was executed in two phases. The first phase consisted of intervention development and refinement. Intervention development was accomplished by conducting three focus groups with counselors and patients of a chemical dependency treatment center for women in which standard MBRP is a required part of programming. The purpose of these focus groups was to gather themes associated with trauma and substance use (e.g., avoidance of PTSD symptoms and function of substance use as it relates to PTSD, craving, guilt/shame, self-esteem). Information gathered after each Phase I focus groups was integrated into the standard MBRP protocol, along with aspects of CPT. Each protocol modification was presented to participants at subsequent Phase I focus group meetings for feedback and further refinement of the protocol until a final pilot adaptation was created. The pilot protocol underwent three revisions with participants' feedback. Phase II of the study consisted of a feasibility and initial efficacy trial using the refined intervention, and collection and assessment of feasibility and preliminary outcome data.

Phase I: Intervention Development and Refinement

Counselors and residents from the Volunteers of America Women's Residential Center (WRC) were recruited for a series of focus groups to assist with the development and refinement of TI-MBRP. Attending separate groups to ensure confidentiality, counselors and residents with previous experience in MBRP groups discussed how trauma-related symptoms and issues have

manifested during MBRP sessions, and offered suggestions, reflections, and concerns regarding the appropriateness and acceptability of integration of trauma education and treatment approaches into MBRP. Information collected during these focus groups informed the initial adaptation of the intervention.

Following these focus groups, protocol revisions were made by the Principal Investigator, and presented to counselors, residents, project mentors, and consultants for further input; a finalized protocol was developed, resulting in the TI-MBRP protocol and treatment manual used in the feasibility and initial efficacy trial.

Trauma Informed- Mindfulness-Based Relapse Prevention. TI-MBRP is an eight-session intervention that integrates trauma education and treatment approaches of CPT (Resick & Schnicke, 1993) into the standard MBRP protocol (Bowen, Chawla, & Marlatt, 2010). TI-MBRP honors the foundations of mindfulness meditation practice and cognitive-behavioral techniques of MBRP while introducing PTSD education and trauma processing surrounding five primary themes from CPT: Trust, Safety, Power and Control, Esteem, and Intimacy. Each TI-MBRP session included mindfulness practices that bring awareness to cognitive and behavioral processes underlying substance use, and how substance use functions as a mechanism to cope with PTSD symptoms. Sessions build upon content and practices in previous sessions, as participants become more aware of factors underlying their substance use and develop skills for responding to triggers or high-risk situations more effectively. The goal of TI-MBRP is to educate women in chemical dependency treatment settings about the interrelationship between substance use and trauma, support trauma processing with present-centered awareness via mindfulness-based exposure/response prevention practices, and prepare participants to skillfully respond to high-risk situations that increase risk of relapse.

Phase II: Feasibility, Acceptability, and Initial Efficacy

Trial Selection of participants and sampling. Participants were recruited from Hazelden Betty Ford Foundation (HBFF) and Lifeworks NW in the Portland metro area, which offer inpatient and intensive outpatient (IOP) treatment for SUD. Facilities under HBFF included one residential and one IOP clinic, and facilities under Lifeworks NW included two residential and one IOP clinic, totaling five clinics. Criteria for admittance into all facilities include a dual-diagnosis for substance use disorder (SUD) and another mental health disorder. Approximately 95% of women within these treatment facilities have a lifetime history of trauma, and approximately 88% are dually diagnosed with SUD and PTSD. As part of the standard care at the residential sites at HBFF and Lifeworks NW, patients undergo a detoxification treatment phase upon admission, followed by a “core learning” phase in which patients participate in group and individual therapy. They then move into a “transition phase” during which they prepare an aftercare plan, and secure both sober housing accommodations and partial employment and/or enrollment in an educational institute or trade school. Patients enrolled in HBFF and Lifeworks NW IOP have already undergone detoxification and are required to participate in groups, individual therapy and case management; treatment completion is between eight and 12 months.

Patients in the core learning phase of residential treatment, and patients in IOP were recruited for the study. Patients in residential programs were physically stable after the detoxification phase, and able to participate in groups. The core learning phase of treatment within residential facilities typically begins two to three weeks after detoxification and lasts for approximately three months. Counselors and administrators of both residential and IOP clinics assisted with recruitment via word of mouth, flyers, and announcements at weekly group meetings. Data was monitored during the recruitment process and additional effort was made to

recruit ethnic and racial minority groups when necessary. To be included in the study, individuals 1) were in the “core” phase of treatment or in IOP at LWNW or HBFF; 2) scored at least a four or higher on Breslau’s Short Screening Scale (Kimberling et al., 2006) for PTSD; 3) were between 18 and 70 years of age; 4) were fluent in speaking and reading English; and 5) had clearance from appropriate clinical staff. Individuals were excluded from study participation if they 1) endorsed active suicidality, hallucinations, or intense emotional lability; 2) had already participated in an MBRP group in current or past treatment; and 3) did not provide informed consent. Inclusion and exclusion criteria were assessed by the Inclusion/Exclusion Screening Tool.

Sample size estimation. For a fully-powered, cluster-randomized design, a power analysis conducted via G*Power (Faul, Erdfelder, Lang, & Buchner, 2007) using $\alpha = .05$, medium effect size across primary outcomes, mediators and moderators, a variance inflation factor of 2.55, and power level of .8 suggests a sample size of 437 participants (Donner, 1998). As a feasibility and initial efficacy trial, it is justified to recruit 10% of what is required of a fully powered clinical trial (Cocks & Torgerson, 2013; Treece & Treece, 1977); thus, we aimed to recruit 44 participants. Due to high attrition rates (56%) at a 15-week follow-up from previous research at the Phase I clinical sites (Witkiewitz, 2014), we aimed to recruit 100 participants to secure a sufficient sample size at one-month follow-up powered to analyze primary outcome data at the end of intervention implementation. We aimed for an attrition rate of 40% or less due to the short duration of the study and greater ease in contacting participants at follow-up due to most participants’ residential and active IOP status. Mediators and moderators were not included in the power analysis due to the current study being a feasibility and initial efficacy trial, and the

exploratory intention of examining mechanisms and moderators for a future, fully-powered study.

Personnel involved in the study. The study PI and three advanced graduate-level Research Assistants (RAs) were responsible for pre- and post-intervention focus groups. TI-MBRP manual adaptation was informed by input from CPT literatures, primary mentors, WRC staff and patients, and consultants. The PI and RAs delivered either TI-MBRP or Standard MBRP. In addition to three RAs who served as study interventionists, three additional graduate-level RAs assisted with data collection at each assessment time, totaling six RAs throughout the study. Before implementation of the study, RAs responsible for implementing interventions completed an advanced teacher training in MBRP. Those who facilitated TI-MBRP attended the MBRP teacher training and an additional training in the TI-MBRP protocol. RAs responsible for implementing standard MBRP did not receive training in TI-MBRP to account for possible contamination effects by Standard MBRP interventionists. All RAs attended a training in implementing study protocol and procedures, which included training on recruitment and screening; assessment collection, entry, and storage; protocols for adverse events; and contacting participants throughout the study. Counselors from study sites were involved in the screening and recruitment of participants for the study. All study personnel completed a protection of human subjects course and HIPAA course prior to contact with any participants and involvement in the study.

Procedures. Interested patients in IOP or in the core phase of residential treatment were screened for eligibility based on the Inclusion/Exclusion Screening Tool, BSSS (Kimberling et al., 2006), and had clearance from appropriate clinical staff. Individuals who signed up for the study were asked to complete the Inclusion/Exclusion Screening Tool and BSSS. If they

endorsed a four or higher on the BSSS and met inclusion criteria, they were offered participation in the study. Interested patients also had clearance from their primary counselors to confirm they did not meet exclusion criteria. Eligible individuals were provided with a written and oral informed consent. The PI or RA reviewed the informed consent and answer any questions or concerns that individuals had about study procedures, confidentiality, data analysis, and dissemination of results. Once written informed consent was obtained, participants were notified of the group start date within one week of signing the consent form. Participants were asked to complete a battery of paper-and-pencil assessments within one week prior to the start of the first session. After assessments were completed, cohorts of participants were randomized to receive either Standard MBRP or TI-MBRP. A non-interventionist RA used computer randomization software to assign to cohorts to either Standard MBRP or TI-MBRP. Ten TI-MBRP and Standard MBRP groups were implemented simultaneously at five sites for maximization of participants within the given timeframe over a 12-month period.

After the first Standard MBRP and TI-MBRP session, participants were provided with a CD player and CD with audio-recordings of guided meditation practices used in the intervention (i.e., body scan, breath awareness) to use daily as a part of their homework requirements. Cohorts randomized to the TI-MBRP group were given an additional CD with mindfulness practices administered only in the TI-MBRP course.

Participants completed a post-course assessment battery within one week of the completion of the eight-session course, taking place over four weeks. They had access to doctoral level psychology graduate students and to their primary counselor to discuss any distressing feelings related to the study.

One week after post-course assessments, participants were invited to participate in a focus group to discuss what was helpful about the intervention and what could be changed. Focus groups were audio-recorded, transcribed, and analyzed in NVivo Pro V12. Frequently discussed topics within focus groups were used to inform changes to the pilot protocol which will optimize interventions within TI-MBRP targeting craving, substance use and PTSD symptoms.

One month after the completion of post-course assessments, participants were asked to complete a follow-up assessment battery. If participants were unable to be physically present to complete the follow-up assessment, they were offered a phone interview during which an RA administered self-report assessment measures orally.

Participants were given a \$20 gift card (not redeemable for alcohol, cigarettes, or lottery tickets) at completion of each of the first two assessments (i.e., baseline assessment, post-course assessment) and post-course focus group. A \$40 gift card was provided at completion of the one-month follow-up assessment. Total possible compensation for participation in the study was \$100.

Design and analyses. This study is an initial step in exploring the safety, feasibility, and acceptability of a novel adaptation to an evidence-based intervention. We employed a cluster-randomized, mixed methods, repeated measures design to determine feasibility, acceptability, initial efficacy, and mediators and moderators for TI-MBRP for women with co-occurring SUD and PTSD. Data from this study will inform the ecological validity and any further modifications that need to occur to the adapted protocol before conducting a larger cluster-randomized trial (Leon, Davis, & Kraemer, 2011; Moore, Carter, Nietert, & Stewart, 2011). Furthermore, determining initial efficacy and mediators and moderators will inform whether integrating

evidence-based trauma education and interventions into MBRP will reduce PTSD symptom severity and substance use indices in dually diagnosed women with PTSD-SUD more efficiently than SUD treatment alone, and inform which measures to test as mechanisms and moderators in a larger trial (Leon, Davis, & Kraemer, 2011).

Paper-and-pencil, self-report measures used at baseline, post course, and follow-up assessment points, as well as records of attendance, were double-entered into SPSS 26.0 by RAs. Prior to conduction planned quantitative analyses, data was checked for normality (skew +/- 2, kurtosis +/-2), homogeneity ($p < .05$), and accuracy using the exploratory function in SPSS (Fields, 1999). Outliers were assessed by identifying studentized residuals greater than ± 3 standard deviations. Although missing data is expected in this population, Restricted Maximum Likelihood Estimations (RMLE) allow for all participants to be included in analyses even if they present with missing data.

Feasibility and acceptability was assessed using multiple metrics. Based on completion rates of an RCT conducted at the Phase I clinical site (Witkiewitz et al., 2014), we assessed recruitment and retention rates, with a target rate retention of 60% or better. Participant overall course satisfaction was measured by the OCSS. Treatment dropout was monitored by tracking attendance at each session and information will be gathered from clinical sites to determine whether the participant dropped out of treatment altogether or the study. This will allow assessment of any systematic bias or characteristics of TI-MBRP drop-outs vs. course completers.

To assess initial efficacy, Repeated Measures Analysis of Variance (RM ANOVA) was used to examine differences between TI-MBRP and Standard MBRP in substance use, craving, and PTSD symptoms over time. When an interaction effect was detected, an ANCOVA was used

to determine the timepoint in which two conditions differed, controlling for baseline scores (Fields, 1999). Mediators and moderators were examined using PROCESS in SPSS 26.0 to help identify factors that explain or support change in the relationships between PTSD symptom severity and craving, and PTSD symptom severity and substance use.

For Phase II qualitative data collection and analyses, ten one-hour long focus groups were audio recorded once participants completed either TI-MBRP or Standard MBRP. Women were asked eight questions to assist with the refinement of the pilot protocol (See Appendix .

Questions were as follows:

1. What was your overall experience like in this group?
2. How did this class help with understanding the relationship between substance use and trauma?
3. How did this class help with processing the impact of traumatic events on aspects of your life now?
4. How was this group different or similar from other substance use and trauma groups you have completed in the past?
5. Is there anything that you felt was missing from this program that would have enhanced your experience while taking this course?
6. What aspects of the treatment did you find helpful and/or important in your recovery process?
7. What aspects did you dislike and feel could be changed or taken out?
8. Would you recommend this group to other women who have not taken it yet?
9. How would you describe the group to other women who have not taken this group yet?
10. Are there certain people you would not recommend this group to or think that this group would be inappropriate for?

All audio recordings were transcribed by a third party company, TranscribeMe. Transcribed focus-group data were uploaded into NVivo 12 Pro and coded by the PI and two RAs.. A constant comparison analysis (Fram, 2013; Leech & Onwuegbuzie, 2011) was implemented to code relevant information pertinent to refining the pilot protocol of TI-MBRP, which is recommended for pilot qualitative research (Leech & Onwuegbuzie, 2007). Three coders went through several iterations of extracting themes from transcribed audio recordings on what

women thought the most and least helpful aspects of the program were.

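### The one-month sample is called powered for the primary outcomes, but no stated calculation supports that at 44, 60 or 100 participants

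*Combined protocol and SAP*

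**What the plan says.** All sections cited are in Phase II of the combined protocol and SAP.

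- **Sample size estimation, benchmark.** For a fully powered cluster-randomized design with alpha .05, "a variance inflation factor of 2.55, and power level of .8 suggests a sample size of 437 participants". The effect is described as a "medium effect size across primary outcomes, mediators and moderators", with no numeric value.
- **Sample size estimation, pilot fraction.** Because this is a feasibility and initial efficacy trial, "it is justified to recruit 10% of what is required of a fully powered clinical trial", which gives 44. Earlier attrition of 56% raises recruitment to 100, "to secure a sufficient sample size at one-month follow-up powered to analyze primary outcome data at the end of intervention implementation". The section adds: "We aimed for an attrition rate of 40% or less". It closes by saying that mediators and moderators were left out of the power analysis.
- **Procedures.** "Ten TI-MBRP and Standard MBRP groups were implemented simultaneously at five sites", with assessments after the course and one month later.
- **Design and analyses.** Efficacy is tested by repeated measures ANOVA of the two arms over time. A baseline-adjusted ANCOVA follows when an interaction is detected. Restricted maximum likelihood is said to "allow for all participants to be included in analyses even if they present with missing data". On purpose, the section says that "determining initial efficacy and mediators and moderators will inform whether integrating" trauma content into the standard course improves PTSD symptoms and substance use.

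**The concern.** One paragraph sets the price of 80% power at 437 participants, buys about a tenth of that, and then describes the result as powered for the primary outcomes. The 100 does not close the gap, because it is the 44 grossed up for expected loss.

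The word affects how the results are read. The trial is meant to inform whether the integrated intervention works better. A reader told that the sample was powered could take a non-significant interaction as evidence of no added effect. The plan describes the baseline-adjusted comparison only as a follow-up to a detected interaction. If none is detected, no adjusted between-arm estimate is planned, although that estimate and its confidence interval are what the design of the larger trial needs.

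**Working it through.** **Inputs from the plan:** alpha .05; power .80; variance inflation factor (VIF) 2.55; N = 437; pilot fraction 10%; attrition 56%, with an aim of 40% or less; ten groups; three assessments (baseline, post-course, one month).

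**Assumed, because not stated:** two-sided test; equal allocation; 437 is an unclustered N multiplied by 2.55; ten groups in total over both arms; and, where used, f = .25 for a medium effect, within-person correlation ρ of .3 to .7, and baseline correlation r of .5 to .7.

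**1. The plan's own figures**
- 0.10 × 437 = 43.7, rounded to 44. 44/(1 − .56) = 100. 100 × .60 = 60. This chain is correct.
- 44/437 = 10.1%; 60/437 = 13.7%; 100/437 = 22.9%.
- The 437 itself could not be reproduced. 437/2.55 = 171.4 before inflation. A two-arm comparison at d = 0.5 needs 126 to 128, or 321 to 326 after inflation. One-way ANOVA at f = .25 gives 403 with three groups and 456 with four. Since the test and numeric effect size are not stated, this does not show that 437 is wrong.

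**2. Power scaled from 437** (1 df, same VIF)

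Noncentrality = (1.960 + 0.842) × √(N/437). Power ≈ Φ(noncentrality − 1.960).
- N = 44: 0.889, power 14%
- N = 60: 1.038, power 18%
- N = 100: 1.340, power 27%

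With clustering removed altogether (VIF 1 against 171.4), the figures are 29%, 38% and 57%.

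**3. Power for the planned interaction** (two arms, three time points)

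n = N/2.55; λ = f² × n × 3/(1 − ρ); df = 2 and 2(n − 2); f = .25.

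| N | n | ρ = .3 | ρ = .5 | ρ = .7 |
|---|---|---|---|---|
| 44 | 17.3 | 43% | 57% | 81% |
| 60 | 23.5 | 57.5% | 73% | 92% |
| 100 | 39.2 | 82% | 93% | 99% |

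For 80% power this test needs 38, 28 or 18 participants before inflation. Multiplied by 2.55, that is 97, 71 or 46. The 437 is 4.5 to 9.5 times larger, so this convention did not produce it.

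**4. Expected precision**

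With ten randomized groups in two arms there are 10 − 2 = 8 degrees of freedom between clusters, and t = 2.306. The 95% confidence interval half-width in SD units is t × √(4 × 2.55/N) × √(1 − r²).
- No baseline adjustment: 2.306 × 0.481 = 1.11 at 44; 2.306 × 0.412 = 0.95 at 60.
- r = .5: 0.96 at 44, 0.82 at 60. r = .7: 0.79 at 44, 0.68 at 60.

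A normal approximation would give 0.94 and 0.81 unadjusted, which is too narrow for ten groups.

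**5. Two statements that do not fit together**
- The 437 is described as covering primary outcomes, mediators and moderators. The same section later says that mediators and moderators were not in the power analysis.
- The sentence with the word powered refers both to the one-month follow-up and to the end of the intervention. These are separate assessments, and the number assessed after the course may exceed 44 or 60.

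**The case against.** The strongest reply is that the word may be true for the planned analysis. Under the repeated measures ANOVA with a conventional medium effect and the plan's own VIF, power at 100 is 82–99%, and the plan says likelihood estimation keeps everyone in the analysis. A VIF of 2.55 may also be too harsh: with 4.4 to 6 retained women per group it implies an intracluster correlation of 1.55/3.4 = .46 to 1.55/5 = .31. The sentence excluding mediators and moderators could point to a separate calculation for the primary outcomes alone.

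All of this stands as a limit on the finding. A reader might infer from the 14% and 18% that the trial was badly underpowered. The documents do not support that reading, because the test, effect size and correlation behind 437 are not given and the planned test could do much better. Equally, nothing supports the opposite reading: no such calculation, effect size, correlation or analysis N is stated, and any separate calculation is not shown.

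A second reply is that the section plainly presents a pilot and contrasts it with a fully powered design. That makes misreading less likely but does not correct the word. Nor is the pilot size itself at fault: 44 follows from the stated 10% rule, and the attrition arithmetic is right.

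The conditional ANCOVA is a separate matter that would arise at any sample size, and the plan does not forbid other estimates. It belongs here because those estimates are what a pilot of uncertain power can usefully deliver.

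**Conclusion.** The concern holds as a lack of stated support. The retained sample is 10% to 14% of the only sample size to which the plan attaches 80% power, and nothing is calculated for 44, 60 or 100. Actual power cannot be determined from the documents. It runs from 14–27% on the plan's benchmark (two-sided, 1 df, same VIF) to 43–99% on the planned interaction with assumed f and correlation. That spread is why the word should not stand without its inputs. The inconsistent statements on mediators and moderators, and the mixed time points, add to the uncertainty about what was calculated. The matter is worth correcting, but it gives no reason to change enrolment.

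**What to change.** In Sample size estimation:
- Delete the word powered and say that the sample is a 10% pilot sized for feasibility and estimation. Alternatively, state a calculation tied to the repeated measures ANOVA, with its effect size, within-person correlation, VIF, time point and analysis N.
- Reconcile the two statements on mediators and moderators.
- If precision is quoted, use cluster degrees of freedom. With ten groups and VIF 2.55, the half-width is about 0.95 SD at 60 and 1.11 SD at 44 unadjusted, or about 0.68 to 0.96 SD with an assumed baseline correlation of .5 to .7.

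In Design and analyses:
- Report baseline-adjusted between-arm estimates with 95% confidence intervals at post-course and at one month, whether or not an interaction is detected.
- State that non-significance will not be read as absence of effect.

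The cost is a less favourable stated property and a little more reporting from data already collected. The recruitment target of 100 does not change.

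### The plan relies on REML to keep every participant but ties it to none of its named analyses; run in standard form, the RM ANOVA that decides whether the ANCOVA follows drops incomplete cases

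*Combined protocol and SAP*

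**What the plan says.** All places are in Phase II of the combined protocol and SAP.

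- **Design and analyses, data preparation.** Missing data are anticipated, and the only stated answer is that "Restricted Maximum Likelihood Estimations (RMLE) allow for all participants to be included in analyses even if they present with missing data". No model, covariance structure, random effect or imputation method is named.
- **Design and analyses, initial efficacy.** "Repeated Measures Analysis of Variance (RM ANOVA) was used to examine differences between TI-MBRP and Standard MBRP" on substance use, craving and PTSD symptoms over time. The follow-on step is conditional: "When an interaction effect was detected, an ANCOVA was used" "to determine the timepoint in which two conditions differed, controlling for baseline scores".
- **Design and analyses, mediators and moderators.** "Mediators and moderators were examined using PROCESS in SPSS 26.0".
- **Procedures.** Assessments are at baseline, post-course and one month later. "After assessments were completed, cohorts of participants were randomized to receive either Standard MBRP or TI-MBRP", and "Ten TI-MBRP and Standard MBRP groups were implemented simultaneously at five sites".
- **Sample size estimation.** The full-trial calculation uses "a variance inflation factor of 2.55, and power level of .8 suggests a sample size of 437 participants". The pilot takes 10% of that (44), recruits 100 because earlier research lost 56%, and aims for attrition of no more than 40%. The section refers both to the one-month follow-up and to the end of the intervention as the point of analysis.

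**The concern.** The missing-data statement promises a property that the named methods do not deliver as usually run. A conventional RM ANOVA needs a complete set of scores from each participant. A single-timepoint ANCOVA cannot use a participant who lacks that timepoint's outcome, whatever the estimator. PROCESS fits ordinary regressions on complete cases and does not use REML.

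The RM ANOVA matters most because its interaction decides whether the timepoint comparisons are made at all. If it is complete-case, someone with baseline and post-course scores who misses only the one-month visit has no say in whether the post-course difference is examined. A real difference is then more likely to go undetected, although data bearing on it were collected. As written, a reader cannot tell who is in the efficacy test.

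**Working it through.** **1. The plan's own figure.** 0.10 × 437 = 43.7, rounded up to 44; 44 / (1 − 0.56) = 100. The recruitment target reproduces.

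**2. Who stays in a three-timepoint complete-case test.**
- 40% attrition: 100 × 0.60 = 60. 56% attrition: 100 × 0.44 = 44. These are maxima, since a participant may also miss post-course alone.
- Assume 20% are lost before post-course. Then 80 have post-course scores, of which 80 − 60 = 20 or 80 − 44 = 36 go unused.

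**3. Standard errors, no clustering.** Assumed: outcome SD 1, correlation ρ = 0.6 between any two timepoints, 50 per arm, 40 per arm at post-course, n = 30 or 22 per arm at one month, and dropout unrelated to outcome with no return.
- Complete-case change contrast: √[2(1 − ρ) × 2/n] = 0.231 (n = 30) or 0.270 (n = 22).
- All data, post-course: √{2[(1 − ρ²)/40 + (1 − ρ)²/50]} = √{2[0.0160 + 0.0032]} = 0.196. Ratios 1.18 and 1.38.
- All data, one month: residual variance given both earlier scores is 1 − 2ρ²/(1 + ρ) = 0.55, and the coefficient on post-course is ρ/(1 + ρ) = 0.375. √{2[0.55/n + 0.375² × 0.016 + 0.0032]} = 0.218 or 0.247. Ratios 1.06 and 1.09.
- Sensitivity of the post-course ratios: early loss 10% gives 1.237 and 1.445; 30% gives 1.114 and 1.301. Correlation 0.4 gives 1.191 and 1.391; 0.8 gives 1.166 and 1.362.

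**4. Power of the interaction test, no clustering.** Assume a 0.5 SD difference at both follow-ups (one reading of the plan's unquantified medium effect), α = 0.05, 2 numerator df.
- Complete-case: the differences (0, 0.5, 0.5) have squared deviations from their mean summing to 1/6. Noncentrality (n/2)(1/6)/0.4 = 6.25 or 4.58, with 2(2n − 2) = 116 or 84 df. Power 59% or 45%.
- All data: the two contrasts have the variances above and covariance 2(0.375 × 0.016 + 0.0032) = 0.0184. Noncentrality 8.26 or 7.81, with 240 − 100 − 4 = 136 or 224 − 100 − 4 = 120 df. Power 72% or 69%.

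**5. The planned ANCOVA, no clustering.**
- Post-course: √[(1 − 0.36) × 2/40] = 0.179. One month: √[(1 − 0.36) × 2/n] = 0.207 or 0.241.
- All-data model with baseline means held equal across arms: 0.179 post-course; √{2[0.55/n + 0.00225]} = 0.203 or 0.233 at one month.

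**6. Clustering.** The plan gives a variance inflation factor of 2.55 but no cluster size m. ICC = (2.55 − 1)/(m − 1) is 0.036 if m = 44 and 0.172 if m = 10; both are assumptions. A standard complete-case RM ANOVA with no cohort term, simulated with ten cohorts of ten and no true effect, rejected about 6–7% of the time at ICC 0.036 and about 12–16% at ICC 0.172. The range reflects the two attrition rates and how the cohort variance is introduced.

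**The case against.** The strongest reply is that the established defect is an unnamed estimator, not lost data. The REML sentence stands in the same section as the RM ANOVA, the only repeated-measures efficacy test, and can fairly be read as describing how that test was fitted. This stands in part. The documents neither exclude that reading nor state it, so the loss in the RM ANOVA is conditional. It does not rescue the sentence for ANCOVA or PROCESS, where REML cannot bring in participants with missing outcomes.

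Second, the timepoint estimates come from the ANCOVA, which loses almost nothing (step 5), and the change contrast at one month loses only 6% or 9%. This stands: the cost falls on the interaction test.

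Third, the size rests on assumptions about early loss, correlation and effect, and shrinks under clustering. This also stands. For a cluster-adjusted test (16 denominator df assumed), which is not the RM ANOVA the plan describes, complete-case against all-data power is 43% v 51% and 35% v 50% at ICC 0.036, and 27% v 29% and 24% v 28% at ICC 0.172. If the plan's RM ANOVA had no cohort term, it has the different fault shown in step 6: it rejects too readily.

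A reader might go further and infer that participants were dropped, that the results are biased, or that the trial fell short of its size. The documents support none of these. They do not report who was analysed, they give no evidence that dropout was related to outcome or differed by arm, and 44 retained is the pilot size the plan aimed for.

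**Conclusion.** The point holds in a conditional form and should be fixed. What is certain is that the REML sentence is broader than the named methods allow. What depends on an unstated choice is whether the RM ANOVA was complete-case. If it was, post-course data already collected are unused in the test that controls the timepoint comparisons. Without clustering and under the stated assumptions, power falls by about 13 points at 40% attrition and 24 points at 56%; the loss is smaller in a cluster-adjusted comparison and may be negligible at the higher ICC. Feasibility and acceptability endpoints are unaffected.

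**What to change.** - Fit the efficacy comparison as a REML linear mixed model (SPSS MIXED) on all available timepoints, with arm, time, arm-by-time, a within-person covariance structure, and a cohort random effect with small-sample degrees of freedom.
- Keep the baseline adjustment, either by holding baseline means equal across arms (defensible because baseline assessments came before randomisation) or by using baseline as a covariate for the two later outcomes.
- Report the post-course and one-month contrasts with 95% confidence intervals and the number analysed by arm and timepoint. Dropping the interaction condition is optional.
- Limit the REML sentence to this model, and report the PROCESS models as complete-case with N by arm.
- If the RM ANOVA was already fitted by REML, name the procedure and add the cohort effect if it was absent.

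The document is written in the past tense, so the cost is a modest re-analysis of existing data plus wording; no new data are needed. With about ten cohorts the cohort variance will be estimated imprecisely, and the write-up should say so. If a REML fit with a cohort effect was already used, only wording changes.
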